5.2. Study Rationale

Renal cell carcinoma (RCC) accounts for two percent of all malignant tumors with an age peak between 50 and 70 years of age; men are affected two times more often than women. Due to a lack of effective therapy, locally advanced RCC is the sixth most common cause of cancer-related deaths.

Following the Robert Koch Institute and the Gesellschaft der epidemiologischen Krebsregister in Deutschland e.V. (Society of Epidemiologic Cancer Registries in Germany), approximately 15000 men and women newly developed renal cell carcinoma in Germany in 2012. In contrast to most cancer types, the prevalence rate of RCC worldwide is increasing, with an estimated annual rate of 1.5 - 5.9%.

Approximately 40 - 45% of patients with RCC have "localized" disease (stage I) at the time of diagnosis, 10 - 20% of patients have "localized" disease of stage II, 20% have "locally advanced" disease (stage III) and 20 -30% have "metastatic" disease (stage IV).

In addition, approximately 30% of patients who have "localized" or "locally advanced" disease at the time of diagnosis will develop metastases in the later course.

The lung is the most common metastatic site with 55%, followed by the lymph nodes (34%) and liver (33%) and the skeletal system (32%). Patients with stage II, III, and IV RCC have a 5-year survival rate of 80%, 50 – 60%, and 10%, respectively. 75 – 85% of RCC cases are highly vascularized tumors overexpressing a range of growth factors, such as vascular endothelial growth factor (VEGF), platelet-derived growth factor (PDGF) and fibroblast growth factor (FGF).

Mantle cell lymphoma (MCL) accounts for about five to ten percent of all Non-Hodgkin's Lymphomas (NHL). Most new cases occur at an age of 60 - 65 years, with a majority of male patients (gender distribution about 3:1). Due to the frequently aggressive course and diagnosis often only in advanced stages, the prognosis is poor and a cure by standard chemotherapy is generally not possible.

The incidence rate of MCL is two to three new cases per 100,000 residents annually. Standard of care is immunochemotherapy in combination with rituximab as a first-line therapy. In addition, the importance of high-dose therapy appears to be confirmed for younger patients. Unlike established therapeutic recommendations for first-line therapy, there is no international consensus regarding a recommendation for therapy in a relapsed/refractory situation.

Prognosis of MCL is affected by the stage at first diagnosis (Ann Arbor classification). Only in highly localized stages (I/IE), long-lasting remission may be achieved by radiation therapy. In patients with stage II to IV, the median survival time is approximately three to five years, depending on feasibility of intensive therapy measures. Specifically in elderly patients or patients who cannot receive intensive therapy for other reasons, life expectancy is low: After 5 years, fewer than 15% of these patients survive.

[figure not shown]
Mantle cell lymphomas are characterized by chromosomal translocation t (11;14) (q13;q32) leading to overexpression of cyclin D1 mRNA. Translation of this mRNA is an mTOR-dependent process that is inhibited by the specific mTOR inhibitor temsirolimus.

Gastrointestinal stromal tumors (GIST) are sarcomas that originate in connective tissue of the gastrointestinal tract. They are characterized by the expression of the surface molecule CD117 (c-KIT) and were only identified as a separate tumor entity a few years ago.

GIST are a relatively rare disease in Germany with 1,500-2,000 new cases per year. If detected early, surgery can achieve a complete cure. If the tumor is inoperable or metastatic, it is usually not possible to cure it. In this situation, however, modern drugs such as sunitinib or imatinib mesylate can achieve significantly longer survival with a higher quality of life at the same time, compared to even a few years ago.

Information on Torisel® (temsirolimus)

The antineoplastic agent Torisel® contains temsirolimus (TEMS) as an active ingredient, a specific inhibitor of mammalian target of rapamycin (mTOR) kinase. Temsirolimus is the first mTOR kinase inhibitor approved for tumor therapy. The drug received its initial approval for intravenous treatment of advanced RCC in the first line

in adult patients who had at least 3 of 6 prognostic risk factors. In August 2009, the marketing authorization was also extended for the treatment of relapsed and/or refractory MCL.

Temsirolimus binds to the intracellular protein FKBP-12. The protein-temsirolimus complex binds to and inhibits the activity of mTOR kinase, which plays a key role in the initiation and promotion of cell division. In cancer cells, inhibition of mTOR kinase can block the transcription of genes regulating the cell cycle. This mechanism also appears to be of particular importance in mantle cell lymphoma therapy. In addition, inhibition of mTOR kinase can lead to inhibition of increased expression of vascular cell growth factor (VEGF), which plays a role in the formation of new blood vessels. This can suppress vascularization in the tumor tissue and thus limit blood supply, which does not allow the tumor tissue to receive sufficient blood flow, causing it to die. This mechanism appears to be of particular importance in renal cell carcinoma. Temsirolimus is used according to the Summary of Product Characteristics.

The named contraindications, warnings and precautions for use, side effects, interactions and instructions on the dosage, type and duration of the application should be observed. According to the Summary of Product Characteristics, pre-treatment with an antihistamine is advised. The Summary of Product Characteristics of temsirolimus is part of this observational plan.

Information on Sutent® (sunitinib)

The oral multi-kinase inhibitor Sutent® (active substance sunitinib) is a so-called "small molecule". Sunitinib binds intracellularly to the signal transduction pathways of the cell. This is accomplished by inhibiting multiple receptor tyrosine kinases that are involved in tumor growth, pathological angiogenesis, and formation of metastases.

Sunitinib has direct anti-proliferative effects by inhibiting VEGF and PDGF receptors on the tumor cell. Sunitinib has extensive antiangiogenic effects by inhibiting the PDGF receptors a and ß to pericytes and VEGF receptors 1-3 on endothelial cells.

[figure not shown]
In addition, sunitinib inhibits the receptor tyrosine kinases c-KIT (Stem Cell Factor Receptor), Flt3 (FMS-like tyrosine kinase 3) and RET (Rearranged During Transfection Receptor) and thereby inhibits tumor growth and formation of metastases.

Sunitinib is used according to the Summary of Product Characteristics. The named contraindications, warnings and precautions for use, side effects, interactions and instructions on the dosage, type and duration of the application should be observed.

The Summary of Product Characteristics of sunitinib is part of this observational plan.

Information on Inlyta® (axitinib)

The oral multikinase inhibitor Inlyta® (active substance axitinib) is a "small molecule". Axitinib is a potent and highly selective tyrosine kinase inhibitor of the vascular endothelial growth factor receptors VEGFR-1, VEGFR-2, and VEGFR-3, involved in pathological angiogenesis, tumor growth, and metastases. Axitinib has been shown to be a potent inhibitor of VEGF-mediated endothelial cell proliferation and cell survival. Inlyta® is used according to the Summary of Product Characteristics. The named contraindications, warnings and precautions for use, side effects, interactions and instructions on the dose, type and duration of the application should be observed.

[figure not shown]

The Summary of Product Characteristics of axitinib is part of this observational plan.

Patient Interview Advanced RCC

For the patient interview, the validated FKSI-15 questionnaire and the validated EQ-5D questionnaire/VAS will be used to document the effect of the substances temsirolimus and/or sunitinib and/or axitinib by the patient.

The Functional Assessment of Cancer Therapy-Kidney Symptom Index-15 (FKSI-15) includes 15 questions subdivided into 4 groups. Signs and symptoms, respiratory symptoms, quality of life, emotional symptoms. EuroQol-5D (EQ-5D) includes EQ-5D Index and EQ-Visual Analog Scale (VAS). The EQ-5D in turn is divided into 5 groups: Mobility, independence, usual activities, pain/discomfort, and anxiety/depression.

6. SCIENTIFIC QUESTION AND OBJECTIVE

The treatment of metastatic renal cell carcinoma has undergone substantial changes in a very short time. In recent years, the introduction of various new substances for the treatment of advanced RCC has led to new scientific questions. Temsirolimus and sunitinib are current standard therapies in the first-line therapy of advanced RCC. Temsirolimus is approved for first-line treatment of advanced RCC in adult patients who have at least 3 of 6 prognostic risk factors.

Sunitinib is approved for the treatment of advanced/metastatic RCC. Axitinib has been developed to treat advanced RCC in adult patients after failure of prior therapy with sunitinib or a cytokine.

As of August 2009, temsirolimus is also another therapy option for patients with relapsed and/or refractory mantle cell lymphoma (MCL). In addition, sunitinib is used in patients with unresectable and/or metastatic gastrointestinal stromal tumors (GIST) following imatinib failure or intolerance.

In April 2016, the active substance nivolumab was approved as the first immuno-oncology medicinal product for monotherapy of advanced renal cell carcinoma in adults after previous therapy. In addition, in August 2016, the combination of lenvatinib/everolimus was approved for the treatment of adult patients with advanced RCC after previous treatment with therapy targeted towards the vascular endothelial growth factor (VEGF) and in September 2016, the active substance cabozantinib was approved for therapy of advanced RCC in adults after previous therapy targeting VEGF.

[figure not shown]
Routine use of drugs in routine clinical practice is subject to additional challenges that are generally not fully covered by clinical trials. Therefore, the aim of this registry is to gain an overall picture regarding the efficacy, tolerability, and safety of temsirolimus, sunitinib, or axitinib therapy in patients with advanced renal cell carcinoma, relapsed/refractory mantle cell lymphoma (MCL), and gastrointestinal stromal tumors (GIST) under the conditions of routine use.

In a highly evolving therapeutic setting for advanced RCC, reflected in the current S3 guideline, there is a lack of data from routine use of sunitinib, followed by novel therapy options, followed by axitinib, to assess the efficacy and tolerability of axitinib in the third or later line in a differentiated manner.

Separate evaluations for third line use of axitinib following prior therapy with sunitinib in the first line followed by e.g. nivolumab, cabozantinib, or lenvatinib/everolimus in the second line are urgently needed. The efficacy of axitinib can continue to be documented after directly preceding therapy with sunitinib. These investigations allow a comparison of the efficacy and tolerability of axitinib in different lines.

Therefore, the following information is of particular interest during the course of the investigation:

- Efficacy (maximum response, survival time, progression-free time)
- Treatment tolerability (assessment by physician)
- Safety profile (overall incidence of adverse events and rate of side effects) of patients with advanced RCC, r/rMCL and GIST receiving treatment with temsirolimus, sunitinib, or axitinib
- Profile, comorbidities and characteristics of patients receiving treatment with temsirolimus, sunitinib, or axitinib
- The sequence of systemic therapies for advanced RCC, MCL, and GIST
- Patient interview on quality of life in advanced RCC patients

Temporal sequence

The following time points were defined as the minimum period for the implementation of the registry:

- Patient Recruitment Phase: January 2008 December 2020
- Recruitment rate: 100 patients/year per product
- Average observation period per patient: 6 months for temsirolimus, 12 months for sunitinib, 6 months for axitinib
- Field Phase: December 2021
- Total duration: 14 years + 1 year evaluation and report (2022)

Since the goal is to keep patients in the registry for life, the registry can be continued indefinitely.

The end of data collection is scheduled for December 2021.

7. INVESTIGATION METHODS

7.1. Study design

This is a prospective, non-interventional, observational study. It is planned that a total of 1,600 patients is documented.

Patient Population

Additionally, the purpose of this registry is to document patients in accordance with Amendment III, for which the following criteria are applicable at enrollment:

7.2. Study Setting

Inclusion and exclusion criteria:

- a) Patients with a histologically confirmed diagnosis of advanced renal cell carcinoma without prior therapy and at least 3 of 6 prognostic risk factors or relapsed/refractory mantle cell lymphoma for whom a decision was already made to treat with temsirolimus.
- b) Patients with histologically confirmed diagnosis of advanced/metastatic renal cell carcinoma or unresectable and/or metastatic GIST, after imatinib failure, for whom a decision was already made to treat with sunitinib.
- c) Patients with histologically confirmed diagnosis of advanced renal cell carcinoma after failure of prior therapy with sunitinib or a cytokine for whom a decision was already made to treat with axitinib.
- d) Written informed consent form from the patient is obtained prior to enrollment into the registry.

Due to the non-interventional nature of the registry, no specific requirements apply regarding the management of treatment. Dosing and duration of treatment will be decided by the physician according to individual treatment requirements of the patient.

Extract from the Summary of Product Characteristics

During the treatment of patients with temsirolimus, sunitinib, and axitinib, among other things, the section "Contraindications" of the respective Summary of Product Characteristics must be taken into account. In case of hypersensitivity reactions, the advice in the relevant Summary of Product Characteristics must be observed.

[figure not shown]
- a) In particular, the following excerpts are included under Section 4 "Clinical particulars" of the Summary of Product Characteristics of temsirolimus:
 - Hypersensitivity to the active substance or to any of the excipients of temsirolimus
 - It is recommended that patients be given an H1 antihistamine before an infusion of temsirolimus. In case of known hypersensitivity to antihistamines or in patients who cannot receive an antihistamine for another medical reason, temsirolimus should be used with caution.
 - Concomitant use of substances that affect CYP3A metabolism: CYP3A4 inducers: e.g. dexamethasone, carbamazepine, phenytoin, phenobarbital, rifabutin, rifampicin, St John's wort
 - CYP3A4 inhibitory agents: e.g. atazanavir, clarithromycin, indinavir, itraconazole, ketoconazole, nefazodone, nelfinavir, ritonavir, saquinavir, telithromyzine.
 - Concomitant use of sunitinib
 - Vaccinations
 - Pregnancy.
- b) In particular, the following excerpts are included under Section 4 "Clinical particulars" of the Summary of Product Characteristics of sunitinib:

Dose adjustment:

- Safety and Tolerability: Depending on individual safety and tolerability, the dose can be adjusted in 12.5 mg steps. The daily dose should not exceed 75 mg or drop below 25 mg.
- Dosing interruptions may be necessary depending on individual safety and tolerability.
- CYP3A4 inhibitors/ inducers: Concomitant administration with potent CYP3A4 inducers such as rifampicin must be avoided. If not possible, it may be necessary to increase the dose of sunitinib in 12.5 mg increments (up to 87.5 mg per day for advanced RCC and GIST) under careful monitoring of tolerability.
- Concomitant administration with potent CYP3A4 inhibitors such as ketoconazole must be avoided.
- If not possible, it may be necessary to reduce the dose of sunitinib down to a minimum of 37.5 mg per
 day for advanced RCC and GIST under careful monitoring of tolerability. The use of alternative
 concomitant medication with no or minimal CYP3A4 inducing or inhibitory effects should be
 considered.
- Co-administration of temsirolimus
- Pregnancy.
- c) In particular, the following excerpts are included under Section 4 "Clinical particulars" of the Summary of Product Characteristics of axitinib:
 - The recommended starting dose of axitinib is 5 mg twice daily.

- Concomitant administration of axitinib with strong CYP3A4/5 inhibitors (e.g. ketoconazole, itraconazole, clarithromycin, erythromycin, atazanavir, indinavir, nefazodone, nelfinavir, ritonavir, saquinavir, and telithromycin) may increase plasma concentrations of axitinib.
- Likewise, grapefruit can increase the plasma concentrations of axitinib. It is recommended to select concomitant medication with no or only minimal CYP3A4/5 inhibitor potential. If a potent CYP3A4/5 inhibitor is to be administered concomitantly, an axitinib dose adjustment is recommended. CYP1A2 and CYP2C19 are subordinate pathways (<10%) of axitinib metabolism. The influence of strong inhibitors of these isoenzymes on the pharmacokinetics of axitinib was not investigated. Due to the increased risk of elevated axitinib plasma concentrations, caution should be exercised for patients taking potent inhibitors of these isoenzymes.
- The concomitant use of axitinib with strong CYP3A4/5 inducers (e.g. rifampicin, dexamethasone, phenytoin, carbamazepine, rifabutin, rifapentine, phenobarbital, and hypericum perforatum [St John's wort]) may decrease plasma concentrations of axitinib.
- It is recommended to select concomitant medication with no or only minimal CYP3A4/5 inducing potential. If a strong CYP3A4/5 inducer is required at the same time, an adjustment of the axitinib dose is recommended.
- Concomitant use of axitinib with CYP1A2 substrates may lead to increased plasma concentrations of CYP1A2 substrates (e.g. theophylline).
- Information on pregnancy, lactation, fertility and reproductive function.

8. DATA MANAGEMENT

Data collection and documentation forms

Data collection

The involvement of team members of the medical scientific field sales force (Manager Medical & Science Relations (MSR)) of Pfizer Pharma GmbH ensures that physicians and patients are included in all regions of Germany.

The MSR duties include handing out of the case report forms as well as investigator enrollment. Team members are not involved in the review of patient data to check for the presence of informed consent form or plausibility and completeness. At the end of the field phase, unreturned case report forms may be followed up with the support of MSR.

If a physician agrees to participate in the registry, a written agreement is made with them, specifying the amount of compensation for documentation of a patient. The collection of private addresses of participating physicians is done exclusively for tax reasons based on a landmark decision.

As no clinical and laboratory investigations are performed beyond the usual level, the reimbursement of medical services and medicinal products is paid by health insurance providers. The agreed fee refers to the workload for the provided documentation of treatment in the specified documentation sheet.

Documentation Sheets (CRF)

The report the findings, a special case report form will be provided, which will be completed by the participating physician in a timely manner at the time of enrollment, as well as at the regularly scheduled intervals, according to local guidelines (generally every 8-12 weeks), and at the end of treatment with temsirolimus, sunitinib, and axitinib.

There is an option to document two of the above Pfizer substances on the white or green documentation forms. A pink additional case report form is used to document new therapeutic options in the second line, for example nivolumab, following sunitinib and before axitinib; patient questionnaires are omitted here.

[figure not shown]
Since parts of the logistics (data collection and management, monitoring) are carried out by a contract research organization (Winicker Norimed GmbH, Nuremberg), the documentation should be sent back to the CRO.

Prepared shipment labels will be provided for this. Pfizer Pharma GmbH will pay the costs.

Documentation received by Winicker Norimed will be processed immediately and reviewed for completeness and plausibility of the documentation relating to pre-specified key fields.

If any queries arise, they will be made in writing and directly to the physician. In addition, to assure data quality and verification of documented patient data, it is also planned to conduct monitoring visits at random sites.

A reconciliation of the original patient data from the medical records with the available documentation will be performed. It is ensured that the transfer of all collected data to the Sponsor and to the contract research organization authorized to perform the evaluation will be performed in pseudonymized form in accordance with the federal data protection laws.

When signing the registration to participate, the physician declares their consent to the original data comparison. Since this work requires additional time from the monitoring physician, a separate lump sum per visit is scheduled for this.

Data storage

To enable inspections and/or audits by regulatory authorities or Pfizer, the study site agrees to keep all records: the identity of all participating patients (sufficient information for the unique attribution of the data, e.g. CRFs and patient files), all signed informed consent forms, copies of the CRFs, completed serious adverse event forms, source documents, all detailed treatment notes and study-related correspondence (e.g. letters, meeting/telephone call logs). All records will be kept by the study site in accordance with applicable regulations, however for at least 10 years.

If for any reason the study site becomes unable to retain the study records for the required period (e.g. retirement, relocation), Pfizer should be notified in advance. The study records must be transferred to another entity authorized by Pfizer, such as another site, another practice, or an independent third party appointed by Pfizer. Prior to disposing of the study documents, the study site shall notify Pfizer in writing, even after the retention period has elapsed.

Quality Control:

In a data validation plan (DVP), audits are defined for plausibility of the recorded data. As far as possible, these audits will be supported by programs, and queries will be submitted to sites by the CRO for deviations.

Outcome and query resolution will be tracked and data changes are performed in the database as applicable. All changes performed are logged in an Audit Trail File.

In addition, to assure data quality and verification of documented patient data, monitoring visits are planned at random selected sites.

Other aspects: Not applicable.

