The evaluation of therapy response is to be performed according to the Response Evaluation Criteria in Solid Tumors (RECIST) as follows whilst following the below-mentioned measurement conditions:

- Use of consistent metric information (here: height in mm)
- Use of consistent imaging procedures (method and technique, e.g. CT)
- Measuring in a uniform manner. The following procedure should be followed:
- It is intended to select the 5 largest indicator lesions that can be measured well; the greatest longitudinal diameter is measured in each case
- Lesions that have a size of at least ≥20 mm in at least one direction are deemed measurable
- Exception: Magnetic resonance imaging; minimum size ≥10 mm required
- All other lesions will be documented without measurement of size.

For the overall tumor assessment, definitions will be applied according to RECIST:

		Target lesions	Non-target lesions
Complete remission	CR	Complete disappearance of all lesions	Complete disappearance of all lesions
Partial remission	PR	Reduction of the measured total by at least 30%	-
Stable disease	SD	Neither PR nor CR or PD	-
Progression	PD	Enlargement of the measured sum by 20% or one or more new lesions	One or more new lesions. Definite enlargement of existing lesions

Verification by imaging procedures after at least four weeks is required to assess a "confirmed" CR and PR.

For the assessment of a "confirmed" SD, the assessment must meet the established criteria at least once over the course of \geq 6-8 weeks.

Documentation during the treatment course

The physician will be provided with an indication-specific documentation sheet for each patient to document the findings for the duration of the observation. Data are collected entirely prospectively; i.e. documentation of previous treatment courses is not allowed.

[figure not shown]
The dose and duration of treatment with the documented medicinal products will be specified by the treating physician according to clinical and individual requirements.

To provide accurate information on the treatment mode of temsirolimus, sunitinib and axitinib, the loading dose at the start of the observation and any changes during the observation period are documented, indicating the time points, current dose and reasons for change.

Each concomitant medication will be used at the discretion of the treating physician and will be recorded in the case report form upon enrollment.

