6 ENDPOINTS AND COVARIATES

6.1 EFFICACY/EFFECTIVENESS ENDPOINT(S)

Variable	Role	Operational definition		
Overall survival	Outcome	presented in months		
Progression free survival	Outcome	presented in months		
Response to therapy	Outcome	according to RECIST / according to Cheson (for MCL)		
Physician's global assessment	Outcome			
Karnofsky performance status	Outcome Subgroup identifier	not for MCL		
ECOG performance score Outcome Subgroup identifier		only for MCL		

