In case an event (either death or progression) was present and date of event was documented, the following definitions was used:

Overall Survival (OS, months) = $\frac{\text{date of death} - \text{date of baseline visit} +1}{365.25 *12}$

Progression Free Survival (PFS, months) = (minimum of (date of death, date of progression) – date of baseline visit + 1)/365.25 * 12.

In case information on dates were partly or completely missing or contradictory, the following was done:

• PFS:

- o the presence of a progression was confirmed, but no date was documented: if date of last intake of study medication was given, this date was used as date of progression, otherwise the date of the last visit with a documented "non-progression (e.g. SD)" was used as date of progression.
- o the presence of a progression was confirmed, but dates within a visit and on final documentation were contradictory, the prior date was used.
- o in case a death was documented within a survival follow-up/ within sequence 2 for subjects from sequence 1, but no progression was documented within regular study, the date of last visit + 1 day was used as date of progression.
- o in case no progression was documented, subject was censored with the latest available contact date / assessment date within study/within sequence.
- o in case these rules led to a missing duration or a negative duration, duration was set to "1 day".

• OS:

- o in case a death was documented, but date of death was unknown, the date of death was substituted with the latest available date for the patient (last visit, last contact date, date of assessment)
- o in case no death was documented, subject was censored with the latest available contact date / assessment date within study.
- o in case these rules led to a missing duration or a negative duration, duration was set to maximum of (PFS,"1 day").

Response to therapy (Recist criteria/ Cheson criteria)

Response to therapy according to the Recist/ Cheson criteria will be analyzed using the physician's assessment as documented in the CRF. As neither "size of lesion", "new lesions" or "increase in size" are defined as key fields, contradictory answers will not overvote physicians assessment.

"Best response" will be analyzed using the physician's assessment at final visit. If "Best response" is missing it will be determined from the best response documented during previous follow-up visits.

Treatment

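### Response and PFS labelled RECIST rest on a physician rating that stands even when a documented new lesion contradicts it, and no planned table shows how often this happens

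*Protocol*

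**What the plan says.** **Definition.** Protocol section 11 (Efficacy Criteria) has response evaluated by RECIST. Its table gives, for progression in target lesions, "Enlargement of the measured sum by 20% or one or more new lesions"; a new lesion is also progression in the non-target column. SAP 6.1 defines the response outcome as "according to RECIST / according to Cheson (for MCL").

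**Analysis.** SAP A1.3 (Response to therapy) says that response "will be analyzed using the physician's assessment as documented in the CRF". It adds that, since none of lesion size, new lesions and increase in size "are defined as key fields, contradictory answers will not overvote physicians assessment". Best response is the physician's assessment at the final visit or, if that is missing, the best rating from earlier follow-up visits. PFS (A1.3, Survival) runs to the earlier of the documented dates of death and progression. The rules for missing or conflicting dates do not mention the lesion fields.

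**Data checking.** Under Protocol section 8, forms arriving at the CRO are "reviewed for completeness and plausibility of the documentation relating to pre-specified key fields". Under Quality Control the same section adds a second layer: "In a data validation plan (DVP), audits are defined for plausibility of the recorded data", and "As far as possible, these audits will be supported by programs, and queries will be submitted to sites by the CRO for deviations". It also provides for comparison with the medical records, with monitoring visits at randomly selected sites.

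**The concern.** The registry collects the information that decides progression under its own table and then gives it no role in the analysis. The reason given is the data-management status of the fields, not a clinical argument. A visit with a new lesion on the form and a rating of SD or PR stays SD or PR, and the result is still reported as RECIST.

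The SAP treats comparable conflicts differently. Contradictory progression dates resolve to the earlier date, and implausible laboratory values have listed queries and cut-offs. For lesion fields against the rating, neither SAP section 8 nor the legible part of the table list in SAP section 9 contains a count or a sensitivity analysis.

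Maximum response and progression-free time are stated objectives in both documents. Protocol section 11 (Discussion of potential bias sources) also plans a comparison of efficacy between the three drugs. That discussion names selection bias and confounders but not response assessment. If discordance differs by drug, the comparison is affected and nothing in the output would show it.

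**Working it through.** The plan states no figure on this point, so there is nothing to reproduce. The check is a trace through the rules, followed by an illustration of size.

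**Trace.** Take a visit with a new lesion documented and a rating of SD. The Protocol's table makes it PD. Under SAP A1.3:

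| What happens next | PFS under A1.3 | Effect against the Protocol's table |
|---|---|---|
| PD first recorded, with its date, at the next visit | event at the next visit | about one visit interval late |
| Physician later enters the true progression date | event at the true date | none |
| Progression confirmed but undated, no last-intake date, and this is the last non-progression visit | event at this visit | none |
| This is the last visit; death recorded in survival follow-up | event at last visit + 1 day | 1 day late |
| This is the last visit; no progression or death ever recorded | censored at latest contact | progression missed |

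So the effect of this contradiction ranges from none to a missed event, and it never brings progression forward.

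**Best response.** The misrated visit matters if no rating of SD or better came earlier. The patient then moves from PD to SD, or to PR if rated PR. An SD rating leaves the CR+PR rate unchanged and raises only SD and clinical benefit. A PR rating with a new lesion can raise CR+PR.

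**Illustrative size for PFS.** Inputs:
- Visit interval: 8 to 12 weeks (SAP A1.1).
- f, the share of progressions recorded one visit late: assumed 5–20%.
- q, the share recorded one visit early (PD rated without lesion support): assumed 0–20%.

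The documents give neither f nor q. The calculation treats every progression as observed and every error as exactly one interval, so the trace above shows it to be an upper case for late recording.

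Interval in months: 8 × 7 / 365.25 × 12 = 1.84; 12 × 7 / 365.25 × 12 = 2.76.

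Shift in mean PFS = (f − q) × interval:
- f = 5%, q = 0: 0.05 × 1.84 = 0.09 to 0.05 × 2.76 = 0.14 months longer.
- f = 10%, q = 0: 0.18 to 0.28 months longer.
- f = 20%, q = 0: 0.37 to 0.55 months longer.
- f = 10%, q = 10%: 0.
- f = 10%, q = 20%: 0.18 to 0.28 months shorter.

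The sign therefore depends on two rates that only the registry's own data can supply.

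**The case against.** The strongest reply is that this is an openly declared choice. Protocol section 11 lists the physician's assessment of response as an efficacy criterion, imaging is routine and recorded only if available, the evaluation is descriptive, and SAP 4.1 and 4.2 set no hypotheses or decision rules. That stands. It supports keeping the physician's rating as the main analysis, but it does not justify the RECIST label or the absence of a count.

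Three stronger readings are tempting, and the documents do not support them.

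- **That only key fields are checked, so these forms are never queried.** The key-field limit applies to the CRO's intake review. The data validation plan covers recorded data without that limit and leads to queries, SAP section 7 mentions edit checks and queries, and there is source comparison: "A reconciliation of the original patient data from the medical records with the available documentation will be performed". The validation plan's content is not in the documents, so whether it cross-checks lesion fields against the rating is unknown. A1.3 says that contradictions do not override the rating; it does not say that they go unqueried. Equally, nothing shows that they are queried, and a rule for contradictions present at analysis suggests that some were expected to remain.
- **That response and PFS are overstated.** The no-override rule also preserves a PD rating without lesion support, and two of the PFS date rules place events early. Part of that reverse group is no contradiction at all, because PD may rest on definite enlargement of non-target lesions, which are not measured.
- **That PFS is lengthened by at least one visit interval.** The trace shows outcomes with no shift or a shift of one day.

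Table 2.1-2 also separates confirmed from unconfirmed best response (except for temsirolimus in MCL), which partly limits the effect of a single misrating.

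**Conclusion.** The point holds in a limited form. In the analysis, a documented new lesion does not change a rating of SD or PR, so outcomes labelled RECIST can contradict the registry's own RECIST table. For that contradiction the direction is fixed: progression can be delayed or missed, and best response can be too favourable. Over all discordant forms, both the net direction and the size are unknown. The 0.09–0.55 month range for mean PFS rests entirely on an assumed 5–20% of late recordings with none early; it is an illustration, not an estimate. Importance is low: the effect is probably modest and no formal decision depends on it. It does bear on what the registry may say about response and PFS, and on any comparison between drugs.

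**What to change.** 1. Keep the physician's rating as the main analysis and label response and PFS as physician-assessed in SAP 6.1 and in the tables.
2. Tabulate, by drug, the visits where the lesion fields and the rating disagree, in both directions: new lesion with a non-PD rating, and PD rating without lesion support. Footnote that the second group may include progression in unmeasured non-target lesions.
3. Add a sensitivity version of Tables 2.1-2 and 2.3-1 for mRCC and GIST in which the first visit with a documented new lesion counts as progression. MCL is left out because it is assessed by Cheson.
4. State whether the data validation plan already cross-checks these fields. If a check is added, make it a programmed one on data already in the database, without retrospective re-querying of all earlier forms. Collection began in January 2008 and 200 sites were planned, so going back to sites would not be cheap.

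The cost is a little programming on fields already collected. The sensitivity results will rest on fields that may have been cleaned less thoroughly than the key fields, which should be stated beside them, and they may be slightly less favourable.
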